16.6.3. ABNORMAL INVOLUNTARY MOVEMENT SCALE (AIMS)

The AIMS is a clinician rated assessment of abnormal movements. It contains items related to: facial and oral movements; extremity movements; trunk movements; global judgments and dental status. Seven items of the AIMS range from 0= "None" to 4= "Severe". A score of "mild" (2) in two or more categories or a score of "moderate" or "severe" in any one category results in a positive AIMS score (i.e. the scores are not averaged). The global severity score is the response to "Severity of abnormal movements" found within the global judgments section. Additionally, overall severity is scored on the basis of severity of abnormal movements and incapacitation due to abnormal movements.

The (non-global) AIMS total score is the sum of items 1 through 7. The possible range for the AIMS total score is 0 to 28. Higher values of the total AIMS score indicate increased severity in abnormal movement. If one or more of the AIMS total score items are missing at a visit, the score will be set to missing.

The observed and change from baseline in AIMS total scores to Day 43 will be summarized by treatment.

16.6.4. SIMPSON-ANGUS RATING SCALE (SAS)

The SAS is a measure of extrapyramidal side effects consisting of 10 items: gait, arm dropping, shoulder shaking, elbow rigidity, wrist rigidity, head rotation, glabella tap, tremor, salivation and akathisia. Items are rated on a scale from 0 (normal) to 4 (extreme in severity). The SAS total score is defined as the sum of all 10 items and ranges between 0 and 40. Lower values of the SAS total score indicate milder symptoms. If one or more items are missing at a visit the SAS total score will be set to missing.

The observed and change from baseline in SAS total scores to Day 43 will be summarized by treatment.

Document: ...\ITI\ITI-007\MYA11638\Biostatistics\Documentation\SAP\ITI-007-404 SAP Final V1.0 12JUN2019.docx Author: Version Number:1.0

Version Data

Page 41 of 53

16.6.5. COLUMBIA SUICIDE SEVERITY RATING SCALE (C-SSRS)

The C-SSRS is an instrument designed to systematically assess and track suicidal behavior and suicidal ideation throughout the study. The C-SSRS includes the following four sections: Suicidal Ideation, Ideation Intensity, Suicidal Behavior and Actual Suicide Attempts. The strength of this suicide classification system is in its ability to accurately and comprehensively assess suicidality, while limiting the over-identification of suicidal behavior. The C-SSRS will be administered by a trained rater at the site.

Suicidal Ideation is assessed by 5 questions, the responses to which equate to a 6-point scale from 0="No ideation present" to 5="Active ideation with plan and intent". A score of 4 or 5 on this scale indicates serious suicidal ideation. Any score greater than 0 will be counted as having suicidal ideation.

The Ideation Intensity total score is the sum of five items from the Ideation Intensity scale: frequency, duration, controllability, deterrents, and reasons for ideation. If a subject did not endorse any suicidal ideation, a score of 0 for the intensity total score will be given. The possible range for the Intensity total score is 0 to 25.

The number and percentage of subjects with each type of suicidal ideation or any suicidal ideation during each study period will be summarized. The most severe ideation, the ideation intensity items (frequency, duration, controllability, deterrents, and reasons for ideation), and the ideation intensity total score will also be summarized descriptively.

Suicidal Behavior is collected as actual attempt, non-suicidal self-injurious behaviour, interrupted attempt, aborted attempt, preparatory acts or behavior, suicidal behavior, and suicide. The number and percentage of subjects with each type of suicidal attempt (actual attempts, interrupted attempts, aborted attempts, and preparatory acts or behavior) will be summarized for each scheduled visit and overall by study period. The number and percentage of subjects with any suicidal behavior and those completing suicide will also be summarized for each scheduled visit and overall by study period.

The number and percentage of subjects with suicidality as measured by the C-SSRS will be summarized, where suicidality is defined as having at least one occurrence of suicidal ideation or at least one occurrence of suicidal behavior. The suicidality indicator will be set to 1 if the subject exhibits suicidality for each visit, 0 if the subject does not exhibit suicidality, and missing otherwise. This data will be summarized at each scheduled visit and overall by study period (treatment and post-treatment).

Data collected on actual suicide attempts (lethality of actual attempts and potential lethality of attempts) will be presented in a data listing.

An overall summary of C-SSRS data (post-baseline data across all scheduled visits) will include the frequency and percentage of the following:

- At least one suicidal ideation post-baseline
- Emergence of suicidal ideation (no suicidal ideation at baseline, and any type of suicidal ideation post-baseline)
- Emergence of serious suicidal ideation (no suicidal ideation at baseline, and any serious suicidal ideation [ideation score of 4 or 5] post-baseline)
- Most severe type of ideation post-baseline

Author:

Document: ...\ITI\ITI-007\MYA11638\Biostatistics\Documentation\SAP\ITI-007-404 SAP Final V1.0 12JUN2019.docx

[figure not shown]
Version Number:1.0
Version Date: 12JUN2019

Page 42 of 53

- Worsening of suicidal ideation (most severe suicidal ideation post-Baseline was more severe than it was at baseline)
- o At least one suicidal behavior post-baseline
- Emergence of suicidal behavior (no suicidal behavior at baseline, and any type of suicidal behavior post-baseline)
- o At least one actual attempt post-baseline
- At least one interrupted attempt post-baseline
- At least one aborted attempt post-baseline
- o At least one preparatory acts or behaviors post-baseline
- o At least one instance of suicidality [any ideation or behavior] post-baseline
- Emergence of suicidality (no suicidality at baseline, and any suicidality postbaseline)
- Any completed suicides post-baseline

Document: Author: ...\ITI\ITI-007\MYA11638\Biostatistics\Documentation\SAP\ITI-007-404 SAP Final V1.0 12JUN2019.docx

Version Number:1.0

Page 43 of 53

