8.1.7 Columbia Suicide Severity Rating Scale

The C-SSRS is a questionnaire developed and validated by Kelly Posner and colleagues (2011) for the assessment of suicidal ideation and behavior. Several versions have been developed including the "baseline" and "screening" versions and a combined "baseline/screening" version of the scale which assesses suicidal ideation and behavior in a patient's lifetime and during a predefined time period. This version can assess a patient's lifetime suicidality as well as eligibility based on inclusion/exclusion criteria. A separate "Since Last Visit" version of the scale has been developed which is used to assess suicidality since the patient's last visit. This version is meant to assess patients who have completed at least 1 initial C-SSRS assessment, and should be used in every subsequent visit. The "Since Last Visit" version of the C-SSRS addresses any suicidal thoughts or behaviors the patient may have had since the last time the C-SSRS was administered.

The C-SSRS will be administered by the investigator or an expert site-based rater, as indicated in the Schedule of Events (Appendix A).

At screening, a patient will not be eligible if he or she reports suicidal ideation of type 4 or 5 on the C-SSRS within 6 months prior to screening or any suicidal behavior in the last 2 years prior to screening, as indicated by any "yes" answers on the suicidal behavior section of the C-SSRS.

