9 ASSESSMENT OF SAFETY

9.1 Specification of Safety Parameters

9.1.1 C-SSRS

The C-SSRS will be completed at screening, baseline, and at every subsequent scheduled clinic visit according to Appendix A (Schedule of Events). Details of the C-SSRS are presented in Section 8.1.7.

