7. GENERAL CONSIDERATIONS

Relative Study Day will be calculated from the date of Day 1, which is the day of first treatment with study medication (Study Day 1), and will be used to show the start and/or stop days of treatments, study procedures and assessments, prior, concomitant and post-treatment medications, and adverse events.

- If the date of the treatment, procedure, or event is on or after Study Day 1 date then: Relative Study Day = (date of variable of interest – Day 1 date) + 1.
- If the date of the treatment, procedure, or event is prior to the Day 1 date then:

Document: Author:

Page 14 of 53

Relative Study Day = (date of variable of interest – Day 1 date).

In the situation where the date is partial or missing, Relative Study Day, and any corresponding durations will appear missing in the listings.

Analyses presented by visit or study day will be based on the scheduled visits as planned in the protocol. Visit windows for unscheduled visits or early discontinuation visits are defined in Table A:, which provides the mapping of relative day ranges to the scheduled target days and the study periods. If more than one assessment is available in the same 'Range of Relative Study Days' (window), the assessment closest to the Scheduled Target Day will be selected and assigned to the Scheduled Target Day. If two or more assessments are available in the same window and are equidistant from the Scheduled Target Day, the latest assessment will be selected.

Listings will include scheduled, unscheduled, retest and early discontinuation data.

Table A: Mapping of Relative Day Ranges to Schedule Target Day

| Study Phase | Study Period | | Scheduled Target Day | Schedued Study |
|-----------------|---------------------|---|-------------------------|-------------------|
| | | Range of Relative Study Days | raigot bay | Week |
| Pre-Treatment | Screening | 1-14* days before Day 1 date | Day -14 | -2 |
| Pre-Treatment | Baseline | Day 1 date (definition of baseline varies by assessment – see descriptions below) | Day 1 | 0 |
| Study Treatment | On- Treatment | 2 to 11 days relative to Day 1 date | Day 8 | 1 |
| Study Treatment | | 12 to 18 days relative to Day 1 date | Day 15 | 2 |
| Study Treatment | | 19 to 25 days relative to Day 1 date | Day 22 | 3 |
| Study Treatment | | 26 to 32 days relative to Day 1 date | Day 29 | 4 |
| | | 33 to 39 days relative to Day 1 date | Day 36 | 5 |

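### The overall C-SSRS table is limited to scheduled visits, with one form kept per window, so it can under-count suicidal ideation and behavior rated on unscheduled or early-discontinuation forms

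*SAP*

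**What the plan says.** SAP 16.6.5 defines the overall table with "An overall summary of C-SSRS data (post-baseline data across all scheduled visits) will include the frequency and percentage of the following". Its rows are any-occurrence or worst-value measures: at least one ideation, emergence of ideation and of serious ideation, most severe type, worsening, any behavior, each type of attempt, suicidality and completed suicide.

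SAP 7 gives the general visit rule: "Analyses presented by visit or study day will be based on the scheduled visits as planned in the protocol". Extra visits are then brought in: "Visit windows for unscheduled visits or early discontinuation visits are defined in Table A:, which provides the mapping of relative day ranges". If a window holds more than one assessment, "the assessment closest to the Scheduled Target Day will be selected and assigned to the Scheduled Target Day". If two are "equidistant from the Scheduled Target Day, the latest assessment will be selected". The Day 15 window, for example, is "12 to 18 days relative to Day 1 date". The visible text makes no exception for the C-SSRS.

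Protocol 8.1.7 describes the form used after the initial assessment. It "addresses any suicidal thoughts or behaviors the patient may have had since the last time the C-SSRS was administered". Protocol 9.1.1 sets the timing: "The C-SSRS will be completed at screening, baseline, and at every subsequent scheduled clinic visit according to Appendix A".

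**The concern.** Keeping the assessment nearest to target suits a by-visit mean of a score such as the MADRS, which describes the patient's state around that day. A Since Last Visit C-SSRS form records an interval. Successive forms cover adjoining stretches of time that do not overlap. Dropping one removes a stretch of follow-up about which no later form asks.

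The overall table asks whether an event ever occurred and how severe the worst one was. It should therefore draw on every stretch of follow-up. As worded, it may not. A patient with serious ideation rated at an unscheduled or early-discontinuation visit could be tabulated as having none. Counts in such a table are likely to be small, so one or two patients can change a row.

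**Working it through.** The plan states no figure on this point, so there is none to reproduce. I took the two possible readings of the SAP in turn.

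**Reading 1: scheduled visits taken literally.** Every unscheduled form is excluded, whatever its date. Early-discontinuation forms are excluded as well if that visit is not regarded as scheduled.

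**Reading 2: scheduled days as populated by SAP 7 and Table A.** Inputs:
- Windows from SAP Table A: Day 8 (days 2–11), Day 15 (12–18), Day 22 (19–25), Day 29 (26–32), Day 36 (33–39). Day 43 is left out because its upper limit is not a fixed day.
- Scheduled visit at target −1, 0 or +1 day, the tolerance in the Protocol section 7 visit headings.
- One extra C-SSRS form on any other day of the same window.
- Rule: keep the form with the smaller |day − target|; on a tie, keep the later.

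The windows hold 10 + 4 × 7 = 38 days. Taking away the 5 scheduled days leaves 33 placements for each position of the scheduled visit, and 3 × 33 = 99 in all.

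| Scheduled visit | Extra form dropped, 7-day window | Extra form dropped, Day 8 window | All five windows |
|---|---|---|---|
| On target | 6 of 6 | 9 of 9 | 4 × 6 + 9 = 33 of 33 |
| 1 day late | 5 of 6 | 8 of 9 | 4 × 5 + 8 = 28 of 33 |
| 1 day early | 4 of 6 | 7 of 9 | 4 × 4 + 7 = 23 of 33 |

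Total: 33 + 28 + 23 = 84 of 99 (85%). In the other 15 the extra form is kept and the scheduled form is dropped. Some form is therefore lost in all 99. An extra form that is alone in its window is kept on all 38 days. The 85% is a share of day placements, not of patients.

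**Example, unscheduled visit.** Scheduled Day 15: no ideation. Unscheduled Day 18: ideation score 5. Scheduled Day 22: none since Day 18. Days 15 and 18 share a window. The distances are 0 and 3, so Day 15 is kept. The Day 22 form looks back only to Day 18. In this table the patient has no post-baseline ideation.

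**Example, early discontinuation.** Scheduled visit on Day 15, early-discontinuation visit on Day 17. The distances are 0 and 2, so Day 17 is dropped. Such visits are part of the design: the Protocol Summary and section 4 place them within 1 week of early termination, and Protocol 5.5.2 asks for all end-of-study assessments whenever possible.

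**Direction.** SAP 8 takes percentages from the analysis set unless stated otherwise, so the denominator does not shrink. Removing a post-baseline form cannot create an occurrence, emergence or worsening. In the most-severe row it can only move a patient to a milder category or to none.

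**Scale.** 350 / 2 = 175 per arm, and 1 / 175 = 0.57%. The documents give no rate of unscheduled C-SSRS assessments, so the expected number affected cannot be calculated.

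**The case against.** The strongest reply is that the SAP never says records are windowed before the overall table is derived. The SAP 7 rule opens with analyses presented by visit or study day, and this table runs across visits. That is a fair reading, but it does not rescue the table. Without windowing, the restriction to scheduled visits stands as written and excludes unscheduled forms outright. Neither reading lets every form count.

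Several other points stand and limit the finding:
- SAP 16.6.5 also summarizes ideation during each study period, and behavior and suicidality overall by study period. These are not expressly restricted to scheduled visits and may capture the missing patient. They could then disagree with the overall table, and no rule says how to reconcile the two.
- SAP 7 keeps unscheduled and early-discontinuation data in the listings. SAP 16.6.5 lists data on actual attempts, and SAP 16.1.2 lists deaths from several sources. The records are not lost, although a listing does not correct a summary percentage.
- The visible Protocol 9.1.1 text plans the C-SSRS at scheduled visits. The schedule of events and the table shells cannot be seen. The number of unscheduled forms may be small or zero.

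A reader might infer more: that any positive unscheduled form is automatically lost, that such visits happen because patients are worse, or that the comparison between arms is biased. The documents do not support these. Under the Table A reading, a form alone in its window or nearest to target is kept. No text says why unscheduled visits occur, and nothing shows that omission would differ by arm.

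**Conclusion.** The point holds for one table. As worded, the overall C-SSRS summary can omit a positive unscheduled or early-discontinuation form under either reading, and under the Table A reading it sometimes omits the scheduled form instead. Because each form looks back only to the previous one, the event returns to the table only if it continues or recurs. Any error in the any-occurrence counts is toward under-reporting.

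The 84 of 99 figure assumes two forms in one window, a scheduled visit within one day of target, and equal weight for each day. It shows how the rule behaves and does not estimate how many patients are affected. That number is unknown.

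Elsewhere the SAP follows the principle this table lacks: worst severity and relationship for repeated TEAEs (16.1.1), the worst reading of an ECG triplicate (16.3), and liver criteria over the treatment period and entire study (16.2). The gap should be closed, because the table reports suicidality and the correction is small.

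**What to change.** In SAP 16.6.5, replace the parenthesis that limits the overall summary to scheduled visits with: *all post-baseline C-SSRS assessments (scheduled, unscheduled and early discontinuation), before visit windowing*. Apply the same wording to the by-study-period any-occurrence and most-severe summaries, so that the tables agree. State that the closest-to-target rule of SAP 7 applies to the C-SSRS by-visit tables only; those can stay as planned.

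With this wording, none of the 99 placements loses a form from these summaries. The cost is a short SAP change and one programming filter, with no new data. Reported suicidality counts may rise slightly.

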4 STUDY DESIGN

This is a Phase 3, randomized, double-blind, placebo-controlled, multi-center study to evaluate the efficacy and safety of lumateperone monotherapy in the treatment of patients with major depressive episodes associated with Bipolar I or Bipolar II Disorder (Bipolar Depression). The study consists of the following periods: Screening Period, double-blind On-treatment Period, and Safety Follow-up Period.

Screening Period (2 Weeks)

Potential patients will be evaluated during a Screening Period lasting up to 2 weeks, to ensure sufficient washout of restricted medications. Extension to the screening period may be approved by the Sponsor or representative in extenuating circumstances related to the patient or caregiver.

After obtaining written informed consent, diagnostic interviews and physical examinations will be conducted, vital signs and ECGs will be assessed, and blood samples for laboratory assessments will be collected. Patients considered potentially eligible for participation will be required to discontinue their current antidepressant treatment and/or other psychotropic drugs.

At baseline (Visit 2), patients who continue to meet all eligibility criteria will be randomly assigned to 1 of the 2 treatment arms for a 6-week, double-blind treatment period. Patients will be randomly assigned to 1 of the following groups: 60 mg ITI-007 or matching placebo.

Double-Blind On-Treatment Period (6 Weeks)

Patients will take their first dose of study medication the evening of their baseline visit. A single dose will be taken each day in the evening, with or without food, for the duration of the 6-week On-treatment Period.

Following randomization, patients will attend the clinic on Days 8, 15, 22, 29, 36 and 43.

Safety Follow-up Period (2 Weeks)

A return to the clinic for a safety follow-up visit will occur at Week 8, approximately 2 weeks following the last dose of study medication. If possible, patients who withdraw prematurely will be seen for an early termination visit (within 1 week of early termination) and will be asked to return to the clinic for a safety follow-up visit 2 weeks following withdrawal.

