16. SAFETY OUTCOMES

All outputs for safety outcomes will be based on the SAF Set.

16.1. FOR BY VISIT SUMMARIES OF CHANGE FROM BASELINE SUMMARIES, THE LAST VALUE ON TREATMENT (LAST ASSESSMENT ON OR BEFORE THE LAST DOSE OF STUDY MEDICATION PLUS ONE DAY) WILL BE PRESENTED. ADVERSE EVENTS

Adverse Events (AEs) will be coded using the Medical Dictionary for Regulatory Activities

Document: ...\ITI\ITI-007\MYA11638\Biostatistics\Documentation\SAP\ITI-007-404 SAP Final V1.0 12JUN2019.docx
Author: Version Number:1.0

Version Number:1.0
Version Date: 12JUN2019

Page 31 of 53

(MedDRA) central coding dictionary currently in effect at the time of analysis or database lock.

Treatment emergent adverse events (TEAEs) are defined as AEs that started or worsened in severity on or after the first dose of study medication and on or before the date last dose of study medication plus one day.

All AEs with an onset date after the last dose of study medication plus one day will be listed in the AE data listing and labelled as 'Follow-up Adverse Event'.

See APPENDIX 2 for handling of partial or completely missing dates for AEs. In the case where it is not possible to define an AE as treatment emergent or not due to missing dates, the AE will be classified as the worst case, i.e. treatment emergent.

An overall summary of number of subjects within each of the categories described in the subsections 16.1.1 and 16.1.2 below will be provided as specified in the TLF shells.

Listings will include all AEs, TEAEs and Non-TEAEs. A seperate listing for TEAEs leading to study discontinuation will be presented.

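### C-SSRS emergence and worsening are tabulated only over all post-baseline visits, including the off-drug Day 57 visit; an on-treatment version should be added

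*SAP*

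**What the plan says.** The overall C-SSRS table in SAP 16.6.5 is introduced as follows: "An overall summary of C-SSRS data (post-baseline data across all scheduled visits) will include the frequency and percentage of the following". Its rows include "Emergence of suicidal ideation (no suicidal ideation at baseline, and any type of suicidal ideation post-baseline" and "Worsening of suicidal ideation (most severe suicidal ideation post-Baseline was more severe than it was at baseline", with matching emergence rows for serious ideation, behavior and suicidality. None of these rows carries a period limit.

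Protocol 9.1.1 sets the visits: "The C-SSRS will be completed at screening, baseline, and at every subsequent scheduled clinic visit". Protocol 4 adds that a "safety follow-up visit will occur at Week 8, approximately 2 weeks following the last dose of study medication", and SAP Table A lists Day 57 as a scheduled target day.

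Elsewhere SAP 16.6.5 does split by period. Each type of ideation and any ideation are given per study period. Attempts, any behavior and completed suicide are given by visit and by study period. For the combined suicidality indicator the text reads: "This data will be summarized at each scheduled visit and overall by study period (treatment and post-treatment".

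For adverse events, SAP 16.1 closes the treatment-emergent window "on or before the date last dose of study medication plus one day". Later events are kept apart: "All AEs with an onset date after the last dose of study medication plus one day will be listed in the AE data listing", with a follow-up label.

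**The concern.** Emergence and worsening are the C-SSRS rows that show whether a patient's suicidality became worse than it was at entry. As defined, they mix about 6 weeks on drug with about 2 weeks off drug. A reader of the study report who asks how many patients developed new ideation while taking study drug will find no specified row that answers.

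The by-period tables do not fill the gap for milder ideation. Exclusion 2 in Protocol 5.2 bars a positive answer on ideation Items 4 or 5 but not on Items 1 to 3, so patients may enter with ideation already present. A count of any ideation during treatment therefore combines pre-existing with new cases. At stake is the clarity of a descriptive safety comparison in a depressed population. No formal inference depends on it.

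**Working it through.** **Windows set side by side.**

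| Output | Compared with baseline? | Period |
|---|---|---|
| Any ideation, each type (SAP 16.6.5) | No | By study period |
| Attempts, any behavior, suicide (16.6.5) | No | By visit and study period |
| Suicidality indicator (16.6.5) | No | By visit; treatment and post-treatment |
| Emergence and worsening (16.6.5) | Yes | All post-baseline visits pooled |
| TEAEs (16.1) | Start or worsening on or after first dose | Through last dose plus one day |
| Liver criteria (16.2) | No | Treatment period and entire study |

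Only the emergence and worsening rows are both baseline-relative and without an on-treatment version. The liver criteria show that this SAP already uses a two-window display.

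**Share of off-drug time.** For a completer, 14 of 56 post-baseline days: 14/56 = 25%. For a patient who stops at Week 2 and returns 2 weeks later, 2/4 = 50%.

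**Effect on the arm contrast.** The plan states no C-SSRS rate, so there is no figure to reproduce and every rate below is an assumption. Let p be the on-treatment risk and q the off-drug risk in an arm. The pooled risk is 1 − (1 − p)(1 − q). If q is the same in both arms, the risk difference is multiplied by (1 − q).

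With p = 8% on drug and 4% on placebo (difference 4.0 points, ratio 2.00):

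| Off-drug q, drug / placebo | Pooled risks | Difference (points) | Ratio |
|---|---|---|---|
| 1% / 1% | 8.92% / 4.96% | 3.96 | 1.80 |
| 2% / 2% | 9.84% / 5.92% | 3.92 | 1.66 |
| 4% / 4% | 11.68% / 7.84% | 3.84 | 1.49 |
| 4% / 1% | 11.68% / 4.96% | 6.72 | 2.35 |
| 1% / 4% | 8.92% / 7.84% | 1.08 | 1.14 |

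Over a range of on-drug rates, with equal q of 1% to 4%:
- 4% vs 2%: the ratio falls from 2.00 to 1.66–1.32.
- 12% vs 6%: the ratio falls from 2.00 to 1.86–1.59.
- In both cases the risk difference loses only 1% to 4% of its value.

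With no on-drug difference (6% vs 6%), equal q leaves the ratio at 1.00. A q of 4% vs 1% produces a ratio of 1.41 and a difference of 2.82 points from off-drug events alone.

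**A second model.** Take a constant placebo hazard h = −ln(1 − p8)/8 per week, where p8 is the 8-week placebo risk, and a hazard ratio of 2 on drug only. On-treatment risks are 1 − exp(−12h) and 1 − exp(−6h). Pooled risks are 1 − exp(−14h) and 1 − exp(−8h).
- p8 = 5%: ratio 1.96 on treatment, 1.72 pooled; difference about 3.6 points in both.
- p8 = 10%: ratio 1.92 on treatment, 1.68 pooled; difference 7.0 points, then 6.8.

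Both models agree: with equal off-drug risk the ratio shrinks and the difference barely moves.

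**The case against.** The strongest reply is that most of the C-SSRS plan is already split by period. This is correct. A reader might infer that on-drug suicidality as a whole is mixed with off-drug events, or that a relapse after stopping cannot be recognized. The documents do not support that, because any ideation, behavior and the suicidality indicator are shown separately for the post-treatment period.

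Eligibility narrows the gap further. Items 4 and 5 are excluded at entry, and Protocol 8.1.7 rules out suicidal behavior in the 2 years before screening. If those rules are kept, type 4 or 5 ideation or behavior in the treatment-period tables is nearly always new compared with the recent past. What remains uncovered is mainly new or worsened ideation of milder type, and the emergence and worsening definitions themselves.

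It is also fair that the overall table states its window openly, speaks of post-baseline and not treatment-emergent events, and is a defensible inclusive summary, since an on-treatment table alone would miss events after stopping. C-SSRS and AE counts need not agree even with equal windows, because one comes from a scale at visits and the other from AE reporting. These arguments support keeping the pooled column. They do not argue against adding an on-treatment one.

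Finally, the table shells and the protocol's Appendix A are not available here. The shells may already carry the split, and their absence is not counted as an error.

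**Conclusion.** The point holds in a limited form. The emergence and worsening rows in SAP 16.6.5 cover the off-drug follow-up and have no on-treatment counterpart, unlike the TEAEs, the suicidality indicator and the liver criteria.

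A reader might infer that pooling dilutes the comparison of drug with placebo. That is not established. It is true of a risk ratio when off-drug rates are equal. It is almost absent for the risk difference in that case, and either measure can be inflated or reduced when off-drug rates differ by arm. The SAP plans frequencies and percentages for the C-SSRS, with no test or relative risk; relative risks are planned for TEAEs in 16.1.1. Nor does either document rank these rows as the main suicidality comparison.

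The 25% off-drug share rests on a completer with a 6-week treatment period and a follow-up visit 2 weeks later. All effect sizes above rest on assumed rates. The severity is low: this is a gap in a descriptive safety table that costs little to close.

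**What to change.** In SAP 16.6.5, present the emergence and worsening rows in three columns per arm: on treatment (through last dose plus one day, as for TEAEs), post-treatment follow-up, and all post-baseline visits as now.

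Add a rule that assigns each assessment to a period. Three cases need it:
- An early termination visit may take place up to 1 week after termination (Protocol 4), so its date can fall outside last dose plus one day although its recall covers time on drug.
- The Since Last Visit version (Protocol 8.1.7) can span the last dose, for example when a patient misses the early termination visit and returns only for follow-up.
- The follow-up row of SAP Table A is worded for treatment completers. A patient who stops on Day 14 and returns on Day 28 falls by day range into the Day 29 on-treatment window (Days 26 to 32).

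If the table shells already contain the split, the SAP text need only say so and add the assignment rule. The cost is a few lines of SAP wording and one or two extra columns, with no new data.
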